- Practical demonstration of ability to perform several determinations (at least 5) of the resting motor threshold, under the direct supervision of a physician investigator experienced in rTMS.
- Performing at least the first two rTMS study sessions under the direct supervision of a physician investigator experienced in rTMS.
- Working knowledge of the principles and practices of rTMS and the rTMS device being used in the study, including common side-effects and how to recognize them. Knowledge will be based on completed tutorial sessions with the investigators or rTMS consultant experienced in rTMS.
- Knowledge how to contact the covering physician available in the building.
- Knowledge of seizure first aid, the location of the emergency equipment and medication, how to engage the emergency response system.
- Bachelor's degree or higher.

In addition, a physician with the following qualifications will be readily available in the vicinity if the need arises (in the institute, and immediately available).

Post-treatment Follow-up

Participants will return at 2 weeks and 4 weeks after completion of rTMS for the following measures:

1. Self-reported methadone dose adjustments/changes and other substance use

2. Brief Pain Inventory
3. PEG scale
4. PROMIS-29 pain intensity and pain interference items
5. Hamilton Depression Rating Scale
6. Hamilton Anxiety Rating Scale
7. Patient-rated clinical global impression (CGI) scale
8. Clinician-rated CGI scale
9. Clinician-rated CGI-opioid scale
10. Quality of Life Enjoyment and Satisfaction Questionnaire
11. Visual Analogue Scale (VAS) for Opioid Craving

Statistical Analysis:

The primary effectiveness outcome measure will be proportion of subjects who achieve $\geq 50\%$ reduction in average pain score as measured by VAS and no significant increase in opioid medication use [defined as greater than 25% increase in morphine equivalent dose].

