The effect of rTMS on chronic pain will be performed with a repeated measure ANOVA. Post-hoc contrasts between the groups will be assessed with t tests with correction for multiple comparisons. Groups will be prospectively matched for variables suspected to influence the outcome measures (age, gender, ethnicity). The effect of these variables on each dependent variable will be assessed by ANOVA. In case of significant or near significant effect ($p < 0.10$), these variables will be included in the model (ANCOVA). For all analyses described above, a two tailed probability value of $p < 0.05$ will be selected as significance threshold and correction for multiple comparisons will be applied. In case of nonnormality or inhomogeneity of variance, we will first evaluate data transformation techniques (log or square root) to address these issues. If this cannot be achieved, we will use nonparametric tests, or bootstrap analysis.

Criteria for Early Discontinuation

Subjects will be assessed at least weekly by a study psychiatrist. Subjects will be removed from the study if they experience a worsening of depressive symptoms or an HRSD > 17 . Any answer of “yes” on the Columbia Suicide Severity Rating Scale or a score of > 10 on the Young Mania Scale will require a psychiatric evaluation to determine if continuation in the study is appropriate.

A Clinical Global Impression-improvement score and CGI opioid improvement score will be obtained weekly by a study physician. Subjects will be assessed, by a study physician, for continuation in the study if they score 6 or 7.

Risks associated with the study:

1. MRI scans.

The scan may be dangerous if combined with magnetic objects in the body. While there have been no reports of any harmful long-term effects caused by the MRI scanner, including magnets of high strength, the long-term effects of being placed in a magnet of the strength used in this study is unknown. Subjects with metallic objects in their body which would exclude them from receiving an MRI for clinical purposes are excluded from the

study. Also, although there are no known risks associated with pregnancy, subjects will not be included if pregnant.

2. Reduction in opioid use.

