c. Headache: A mild headache, which responding readily to non-opioid analgesics is the most common side-effect reported in depression treatment trials. All volunteers will be treated with NSAIDs as needed for headache.

d. Hearing Impairment: Rapid excitation of the stimulation coil produces clicks that have resulted in transient increase in the auditory threshold, which does not occur if earplugs are used. A previous study assessed the auditory threshold before and after 30 sessions of rTMS (over 6 weeks) in subjects wore earplugs during stimulation and no significant mean changes were detected. All participants will wear earplugs during the delivery of stimulation.

e. Additional risks include scalp pain, dental pain, and rTMS-induced manic effect. Subjects will be evaluated for each of these and treated with over the counter pain medications if required for the scalp and dental pain. Subjects will also be evaluated for an rTMS-induced manic effect. If mania occurs, they will be removed from the protocol and monitored until these symptoms resolve.

f. Additional risks include scalp pain and rTMS-induced manic effect. Subjects will be evaluated for each of these and treated with over the counter pain medications if required for the scalp and dental pain. Subjects will also be evaluated for an rTMS-induced manic effect. If mania occurs, they will be removed from the protocol and monitored until these symptoms resolve. Convulsive 14 syncope has also been reported, and we will take the following measures to prevent this: participants will be asked to immediately report any symptoms of syncope (e.g. feeling dizzy, light headed, visual changes) and will be placed in the supine position with elevated legs if syncopal symptoms appear.

5. Risks associated with the psychological test battery include potential nervousness and frustration with the tasks. A member of the research team will carefully explain the tests before hand and will be available for questions during the tasks should they arise.

Adverse Event Reporting

Timely, accurate, and complete reporting and analysis of safety information from clinical studies are crucial for the protection of subjects and investigators, and are mandated by regulatory agencies worldwide.

1. Adverse Event Definitions and Classifications

• Adverse Event

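### The primary outcome is a composite responder proportion, but every stated method is for continuous scores; no time point is attached to it, no analysis set or missing-data rule is given, and no pain or opioid assessment is planned after removal

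*Combined protocol and SAP*

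**What the plan says.** **Outcome.** The Statistical Analysis section states: "The primary effectiveness outcome measure will be proportion of subjects who achieve" at least a 50% "reduction in average pain score as measured by VAS and no significant increase in opioid medication use". A significant increase is defined as more than 25% in morphine equivalent dose.

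**Analysis.** The next paragraph begins: "The effect of rTMS on chronic pain will be performed with a repeated measure ANOVA". It continues: "Post-hoc contrasts between the groups will be assessed with t tests with correction for multiple comparisons". Covariates enter through ANOVA or ANCOVA. If normality or equal variance fails, transformation is tried first, then nonparametric tests or bootstrap. The threshold is two-tailed 0.05.

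**Removal.** Criteria for Early Discontinuation says: "Subjects will be removed from the study if they experience a worsening of depressive symptoms or an HRSD" above 17. A positive suicide-scale answer or a Young Mania score above 10 "will require a psychiatric evaluation to determine if continuation in the study is appropriate". The rTMS risk section adds: "If mania occurs, they will be removed from the protocol and monitored until these symptoms resolve".

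**Assessment schedule.** The Brief Pain Inventory is taken at baseline and before each session, and opioid use is asked at each session. The closing scales are given once rTMS is complete. Under Post-treatment Follow-up: "Participants will return at 2 weeks and 4 weeks after completion of rTMS for the following measures".

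**Time point.** Specific Aim 1 hypothesises better pain after five weeks of treatment. The endpoint definition does not repeat this.

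**The concern.** A proportion needs a test or interval for proportions, a denominator and a day of evaluation, and the plan gives none of these. Followed as written, it analyses pain scores and never tests the outcome it calls primary. The opioid condition, which stops pain relief obtained by taking more opioids from counting as success, enters no stated analysis.

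The gap matters more because some subjects will lack outcomes for reasons that may be related to outcome. Removal for worsening mood is plausibly linked to pain and could differ between active and sham. A classical repeated-measures ANOVA drops any subject with a missing score among the time points analysed.

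Two things are at stake. The test, time point and denominator could be settled after the data are seen. And the active-versus-sham contrast could be shifted in either direction, with no stated method for examining this.

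**Working it through.** The plan gives no sample size, power, responder rate or dropout rate, so it has no figure to reproduce. Steps 1 and 2 compare the text with itself. Steps 3 to 5 use assumed inputs.

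**1. Outcome against methods**

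| Needed for the primary outcome | What the plan supplies |
|---|---|
| Comparison of two proportions | Repeated-measures ANOVA, t tests, ANCOVA |
| Use of the opioid condition | None |
| Evaluation day | Five weeks, in the Aim 1 hypothesis only; pain is also scored up to daily in treatment and 2 and 4 weeks after it |
| Denominator | None |
| Handling of missing outcomes | None |
| Pain VAS | Scale lists name the Brief Pain Inventory, PEG and PROMIS-29; the only VAS listed is for opioid craving |

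The nonparametric or bootstrap fallback does not fill the gap. It is triggered by nonnormality or unequal variance, which are properties of continuous scores.

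**2. Data after removal.** During treatment, pain and opioid use are tied to sessions. Later assessments are tied to completion of rTMS, which is undefined for a subject taken off early. The follow-up that is described for such subjects is for safety: mania symptoms until they resolve, and unresolved serious adverse events.

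**3. How far missing outcomes leave the result open.** Let rA and rS be observed responders as fractions of all randomised in each arm, and mA and mS the fractions without outcome data. The active proportion lies in [rA, rA + mA] and the sham proportion in [rS, rS + mS]. Their difference runs from rA − rS − mS to rA − rS + mA, a width of mA + mS whatever the responder rate.

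- 5% and 10%: 0.05 + 0.10 = 15 points
- 10% and 10%: 0.10 + 0.10 = 20 points
- 10% and 20%: 0.10 + 0.20 = 30 points

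**4. The denominator rule matters in both directions.** Assume the same true response p in both arms, so that the true difference is 0.

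- Case A: every removed subject is a non-responder. A completer denominator gives p/(1 − mA) − p/(1 − mS); counting removed subjects as non-responders gives 0.
- Case B: removal is unrelated to response. Completers give 0; non-responder counting gives p(1 − mA) − p(1 − mS) = p(mS − mA).

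| Removal, active v sham | p | Case A, completers (points) | Case B, non-responder counting (points) |
|---|---|---|---|
| 5% v 10% | 10% | −0.58 | +0.5 |
| 5% v 10% | 40% | −2.34 | +2.0 |
| 10% v 20% | 10% | −1.39 | +1.0 |
| 10% v 20% | 40% | −5.56 | +4.0 |

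Swapping the arms reverses the signs, and equal removal gives 0 in both columns. Neither rule is free of bias in general, so one must be fixed in advance and its assumption tested.

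**5. Subjects kept by the ANOVA.** Assume five weekly scores, each missing for 5% of subjects. If missingness is independent, complete cases are 0.95^5 = 77%. If the same subjects miss every score, they are 95%. Removal tends to cluster missing scores, so the truth lies somewhere between.

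**The case against.** **This is a feasibility study.** The introduction says so, and Aim 1 calls the effect on pain and substance use exploratory. The responder proportion could have been meant only for description. This lowers the weight. But the plan does not call the proportion descriptive: it names it the primary effectiveness outcome and sets a 0.05 threshold.

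**A reader might infer that the planned ANOVA would be materially biased by dropout.** This is not shown. In simulations with assumed inputs (no true effect, weekly pain with SD 2, correlation 0.5 to 0.7, about 23% to 27% lost by week 5, loss tied more strongly to pain in one arm), the raw week-5 completer difference was off by 0.06 to 0.16 SD when loss followed the last observed score. That figure fits a week-5 t test or a group main effect. If baseline is one of the ANOVA's time levels, which the plan does not say, its arm-by-time contrast is the completers' change from baseline. That was off by only about 0.01 to 0.06 raw points. A mixed model on all scores was off by 0.04 to 0.13 raw points when loss depended on unseen scores. The documented removals are also triggered by mood, not by pain.

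**A reader might infer that no time point exists, or that outcome collection stops at removal.** The documents support neither. Five weeks is stated in Aim 1 but not attached to the endpoint. Nothing forbids later assessment; none is provided for. A Young Mania score above 10 leads to evaluation, not automatic removal.

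**A reader might count the motor-threshold removals as a further source of bias.** They occur before rTMS begins, so treatment cannot cause them. Whether they precede randomisation is unstated and needs only a clarification.

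**Questionnaires after removal change what removal means.** This stands in part: the sponsor would have to reconcile them with the wording that subjects leave the study.

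**Conclusion.** The point holds and should be fixed. The plan names a composite responder proportion as primary and states no analysis of it. It attaches no evaluation time to it, gives no analysis set or missing-data rule, and plans no pain or opioid assessment after removal.

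The true size is unknown. With assumed missing fractions of 5% and 10%, the responder difference is undetermined over 15 points; with 10% and 20%, over 30 points. These widths hold for any responder rate. The case rests on the unspecified primary analysis and its open denominator, not on a demonstrated bias in the ANOVA. The link between mood-triggered removal and pain outcome, and any difference in it by arm, is plausible but cannot be checked from the documents.

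**What to change.** 1. **Primary analysis.** Compare the composite responder proportion between arms in all randomised subjects at one stated time point (end of treatment is assumed from Aim 1, for the sponsor to confirm). Use a pain scale reconciled with the scale lists, an exact or similar small-sample test, and a confidence interval for the risk difference. Count subjects without outcome data as non-responders. Add a sensitivity analysis that varies their status by arm, because of Case B above. State whether the motor-threshold check precedes randomisation.
2. **Supporting analysis of pain scores.** Use a baseline-adjusted linear mixed model on all available scores, with the end-of-treatment arm difference as the contrast. It keeps partly observed subjects and is valid when loss depends on observed scores. It is not shown to be less biased than a completer change-from-baseline contrast when loss depends on unseen scores.
3. **Data after stimulation stops.** Ask these subjects for the already planned end-of-treatment and follow-up pain and opioid questionnaires, dated from the start of treatment, unless consent is withdrawn. The sponsor should reconcile this with the removal wording. All clinical stopping and removal rules stay with the sponsor.

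**Cost.** New analysis text, a protocol statement and a few extra questionnaires. The reported responder rate will be lower than among completers: if 25% of all randomised respond and 10% to 20% are removed as non-responders, it is 25% instead of 0.25/0.90 = 27.8% to 0.25/0.80 = 31.3%.

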9. Subjects involved in litigation regarding injury or worker's compensation benefits.	9. History, self-report
10. Subjects with a diagnosis of vasculitis, peripheral vascular disease, peripheral neuropathy, small-fiber neuropathy, or fibromyalgia.	10. Medical history, self-report.

Subject Screening:

Subjects will be referred to the study from the Addiction Institute Opioid Treatment Program. Subjects will also be recruited by word of mouth, fliers, newspaper advertisements, and postings on relevant websites. Contact information will be provided so that potential subjects may speak with a research coordinator/research assistant to learn more about the opportunity to participate in the study. Potential participants will take part in a brief phone interview to establish pre-eligibility. Pre-eligible participants will be given an appointment for a screening visit.

They will then undergo additional screening for the study, including a SCID, review of metal implants, pregnancy test (if indicated), medical history, physical exam, vital signs (HR, BP, temp), TASS, and consent for study procedures. For all females of child-bearing potential, a pregnancy test will be repeated prior to beginning rTMS sessions. Daily medication use will be assessed for the 4 weeks prior to study entry using the time-line follow back procedure.

Following screening, the subjects will undergo the following procedures:

- 1) Pregnancy tests will be performed weekly during rTMS and before each MRI. Before the rTMS begins, we will perform an initial determination of motor threshold. Subjects with a motor threshold of 85% (of maximal stimulator output) at the initial determination of motor threshold will be removed from the study. The rationale for this is that, in our experience, high motor thresholds of this level result in discomfort and anxiety when the actual rTMS sessions are delivered.
- 2) Volumetric MRI and MRS scans.
- 3) Baseline neuropsychological testing, including pain scales.
- 4) Five weeks of rTMS, Monday – Friday, on an outpatient basis. The pain scales will be performed during the weeks of rTMS, up to daily.
- 5) Repeat volumetric MRI and MRS scans after the rTMS.
- 6) Repeat neuropsychological tests after the rTMS.

Neuropsychological scales and tests: Subjects will be asked to complete the following tests and scales before and after the sessions of rTMS (at baseline and after the completion of the rTMS).

Scales (expected to take 60 minutes total):

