1. Brief Pain Inventory (at baseline and daily before each rTMS session)
2. PEG scale (at baseline and weekly before each rTMS session)
3. PROMIS-29 pain intensity and pain interference items (at baseline and weekly before each rTMS session)
4. Hamilton Depression Rating Scale (at baseline and weekly)
5. Barratt Impulsiveness Scale (BIS -11) (at baseline)
6. Columbia Suicide Severity Rating Scale (at baseline and weekly)
7. Young Mania Rating Scales (at baseline and weekly)
8. Patient-rated clinical global impression (CGI) scale (at baseline and weekly)
9. Clinician-rated CGI scale (at baseline and weekly)
10. Clinician-rated CGI-opioid scale (at baseline and weekly)
11. Clinical Opiate Withdrawal Scale (COWS) (at baseline and weekly)
12. Quality of Life Enjoyment and Satisfaction Questionnaire (Q-LES-Q) (at baseline and weekly)

Medication use: Subjects will be asked to provide to us the number of medications they took as follows: 1) at baseline (in the week prior to starting sessions); and 2) at each session, where we will ask about opioid and other medication use since the previous session. The amount of opioids used will be converted to oral morphine equivalents and tallied for each day.

Repetitive Transcranial Magentic Stimulation (rTMS): The participants will be randomized into 2 groups: 1) high frequency rTMS (20 Hz), 2) and sham treatment. The rTMS will be administered using the TMS system provided by Brainsway (Brainsway, LTD, Jerusalem, Israel). The rTMS system is equipped with a positioning and cooling system. The positioning system includes a helmet that comprises the coils (which will be either the sham or the H coil), an adjustable arm connected to the helmet, and a device enabling rotation of the helmet around three orthogonal rotation axes. The positioning device enables the accurate and comfortable placement of the coil over the patient's head. The cooling system is designed to maintain ambient temperature in the coils during repetitive operation by allowing streamed the cooled air into the helmet and maintains the coils at ambient temperature.

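### The repeated-measures ANOVA for pain leaves scale, time points, tested effect, missed ratings and sphericity open; run classically on the daily BPI it could exclude many subjects and inflate the group-by-time test

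*Combined protocol and SAP*

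**What the plan says.** The analysis of pain is one sentence in the Statistical Analysis section: "The effect of rTMS on chronic pain will be performed with a repeated measure ANOVA". Between-group t tests with a multiplicity correction follow as post-hoc contrasts. The threshold is given as "a two tailed probability value of $p < 0.05$ will be selected as significance threshold". The assumption checks cover non-normality and unequal variance only, and those two alone trigger the fallback (transformation, then nonparametric tests or bootstrap). The documents contain no missing-data method, sample size or expected rate of missed sessions.

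Several pain series could feed the ANOVA:

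- Daily, in the scales list: "Brief Pain Inventory (at baseline and daily before each rTMS session". Treatment is described as "Five weeks of rTMS, Monday – Friday, on an outpatient basis".
- Also daily, but as a ceiling, in the procedures list under Subject Screening: "The pain scales will be performed during the weeks of rTMS, up to daily".
- Weekly: "PEG scale (at baseline and weekly before each rTMS session", with the same schedule for the PROMIS-29 pain items.
- Follow-up, under Post-treatment Follow-up: "Participants will return at 2 weeks and 4 weeks after completion of rTMS for the following measures".

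The primary outcome is separate and binary: "The primary effectiveness outcome measure will be proportion of subjects who achieve" a set reduction on a pain VAS, without a marked rise in opioid use.

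**The concern.** The BPI is the most frequently scheduled pain scale, so it is a natural input to the ANOVA. Two properties of the classical method then matter.

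First, it needs a complete and equal set of time points for every subject. With 25 weekday outpatient visits, one missed rating removes the subject from the whole analysis, and those left are the best attenders. A schedule that sets a maximum frequency does not promise equal sets.

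Second, its group-by-time F test assumes sphericity. Ratings on adjacent days usually correlate more strongly than ratings weeks apart, which breaks that assumption and makes the uncorrected test reject too often. Neither planned assumption check would detect this.

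At stake is the only named test of whether active rTMS improves pain relative to sham. Because scale, time points and effect are open, they could also be chosen after the data are seen.

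**Working it through.** The plan gives no sample size, miss rate, SD or correlation, so it has no figure to reproduce. All miss rates, arm sizes and covariances below are assumptions.

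**1. Number of ratings.** 5 weeks × 5 days = 25 pre-session ratings; with baseline, 1 + 25 = 26. This is the maximum for the BPI up to the end of treatment. The two follow-up visits would make 28. A weekly scale gives 1 + 5 = 6.

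**2. Share excluded by complete-case deletion.** With a probability m of missing each rating independently, and k post-baseline ratings, the share excluded is 1 − (1 − m)^k.

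| m | k = 25 (daily) | k = 5 (weekly) |
|---|---|---|
| 2% | 1 − 0.603 = 40% | 1 − 0.904 = 10% |
| 5% | 1 − 0.277 = 72% | 1 − 0.774 = 23% |
| 10% | 1 − 0.072 = 93% | 1 − 0.590 = 41% |

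Half the subjects are lost when m = 1 − 0.5^(1/k): about 2.7% for k = 25 and 12.9% for k = 5.

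Clustering of misses within subjects reduces the loss. Under a beta-binomial model with within-subject correlation 0.05–0.17, the complete share for k = 25 is 72–83%, 43–62% and 18–38% at 2%, 5% and 10% missed. The excluded share is then 17–28%, 38–57% and 62–82%.

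**3. Type I error of the group-by-time F test.** Null trials were simulated with complete data, 4000 per setting, at a nominal 5%, with 10 or 20 subjects per arm.

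At 26 ratings, uncorrected, with total variance 1 split into subject effect, AR(1) and noise, and 10 per arm:

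| Subject variance | AR(1) rho | Noise variance | Type I error |
|---|---|---|---|
| 0.5 | 0.7 | 0.2 | 7.7% |
| 0.4 | 0.8 | 0.2 | 10.5% |
| 0.4 | 0.9 | 0.2 | 11.1% |
| 0.4 | 0.9 | 0.1 | 14.1% |

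- Results at 20 per arm are similar, so a fair summary is about 8–15%.
- Pure AR(1) with rho 0.5–0.95, a harsher assumption, gives 9–18%.
- Compound symmetry, where sphericity holds, returns about 5%, as it should.
- A Greenhouse–Geisser correction at 26 ratings brings the error to 0.8–4.8%. It is controlled, but conservative in small samples, and incomplete subjects are still deleted.

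Other readings of the sentence, uncorrected:

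- Six ratings, with the subject-plus-AR(1)-plus-noise covariances carried over to weekly spacing: about 4–7%. If adjacent weeks are instead as strongly correlated as adjacent days were assumed to be, non-spherical settings give 5.5–9.4%.
- Pre/post only: about 5%, since sphericity cannot fail with two time points.
- Between-group main effect: 4–6% in every setting, because it does not use the within-subject error term.

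**4. Size of an alternative model.** Unstructured covariance needs k(k + 1)/2 parameters: 26 × 27/2 = 351 for daily ratings, against 5 × 6/2 = 15 for five weekly means with baseline as a covariate.

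**The case against.** The strongest objection is that no section says the daily BPI enters the ANOVA. Weekly PEG or PROMIS-29 scores, or a pre/post comparison, fit the sentence equally well, and Specific Aim 1 speaks of pain after five weeks of treatment. A schedule with only a maximum frequency even makes a balanced 26-level ANOVA a less obvious reading. The text does not rule out a sphericity correction, and a between-group t test at one time point needs neither sphericity nor a complete series. The study is a feasibility study, pain relief is explored rather than confirmed, and the primary outcome is a responder proportion that this ANOVA does not analyse.

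All of this stands, and it limits the point to a conditional one. It does not remove it: one permitted reading performs badly, nothing in the plan excludes that reading, and the planned assumption checks would not reveal the problem.

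**Conclusion.** The concern holds in conditional form. The pain analysis is under-specified. If it is carried out classically on the daily BPI, it could exclude 40–93% of subjects across assumed independent miss rates of 2–10% (17–82% with clustering), and an uncorrected group-by-time test would run at about 8–15%. On a weekly scale the exclusion is 10–41% and the inflation is small.

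A reader might infer three stronger things that the documents do not support:

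- That most subjects will be lost. No miss rate is given, and at 2% missed the majority remain. Those affected would be left out of one analysis and would not have dropped out of the trial.
- That the p-value will be too small. This applies only to an uncorrected group-by-time test over many time points.
- That the rating before session 1 is treated as an on-treatment value. No section assigns any rating to a level of the ANOVA.

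The change is worth making for the exploratory pain comparison. It has no bearing on the error rate of the binary primary outcome.

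**What to change.** Replace the repeated-measures ANOVA with a linear mixed model fitted by REML to all available ratings, and specify:

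- **Outcome:** weekly means of one pre-named pain score. First reconcile the BPI average-pain item with the VAS named for the primary outcome; the scales list contains no pain VAS.
- **Baseline:** the mean of the ratings taken before the first rTMS session, as a covariate. The rating before session 1 then belongs to baseline and not to the week-1 mean.
- **Fixed effects:** treatment, week and treatment-by-week.
- **Covariance:** unstructured over the five weeks, with Kenward–Roger degrees of freedom and a pre-named simpler structure if the model does not converge.
- **Test:** the week-5 active-minus-sham contrast, which matches the Specific Aim 1 hypothesis.

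This costs a few lines of analysis text and no new data, visits or subjects. The model assumes that ratings are missing at random. That may not hold fully, since subjects can be removed for worsening depression, so the assumption should be stated. A Greenhouse–Geisser correction alone would be a lesser repair, because it still deletes incomplete subjects.
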